Objectives: Primary: To measure the effects that canagliflozin intervention has on reducing average glucose in healthy individuals. Secondary: To assess the tolerability and side effects and urinary glucose excretion following the pulsatile dosing protocol.
Methodology: 
1. Candidates will be offered participation through word of mouth and AgelessRx platform.2. Once screened and enrolled, participants will be randomized into one of two arms (A and B) and provided with all items included in the materials list below.3. Arms A & B:
a Day 0: Participants will attach a continuous glucose monitor (CGM) and follow instructions for calibration period.b Day 1 – 14: Participants will take morning blood pressure readings, and keep dietary intake journal via Lifesum.c Day 7: Participant completes Urine Collection Kit #14. Arm A:
a Day 8 - 14: Participants take 100mg Invokana (canagliflozin) with first meal daily.b Day 15: 24h after final dose, Participant completes Urine Collection Kit #2c Day 16: 48h after final dose, Participant completes Urine Collection Kit #3d Day 17: 72h after final dose, Participant completes Urine Collection Kit #45. Arm B:
a Day 8 - 14: Participants take 150mg Invokana (canagliflozin) with first meal daily, every other day for a total of 4 doses.b Day 15: 24h after final dose, Participant completes Urine Collection Kit #2c Day 16: 48h after final dose, Participant completes Urine Collection Kit #3d Day 17: 72h after final dose, Participant completes Urine Collection Kit #4
Number of subjects planned: Up to 20 healthy individuals via telehealth administration, 10 individuals in each Arm.

Diagnosis and main criteria for inclusion: Subjects will be healthy and of any sex, any ethnicity, and any age from 18-85. Participants must be approved by AgelessRx Medical Team for use of canagliflozin. They also require a CGM-compatible mobile device ([defined here](#))

Test product, dose, and mode of administration (proposed): The tablets will be from the brand Invokana and have a dosage of 100 mg or 300 mg per tablet. Investigational drugs are to be administered orally. Investigational drugs will be provided by Curexa Pharmacy, [name]

Duration of treatment: 7 days

Criteria for evaluation:

Efficacy:

- CGM data
- Urinary glucose

Safety:

- Tolerability

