6.2 Canagliflozin

Canagliflozin is an SGLT2 inhibitor. It is a compound also known under the name Invokana. Canagliflozin is used (with diet and other medications) to treat type 2 diabetes (a condition in which the body does not use insulin normally and therefore cannot control the amount of sugar in the blood). Canagliflozin works by blocking SGLT2, a protein that helps the body reabsorb glucose from urine to the bloodstream. The body instead excretes glucose through urine.¹

Clinical studies

Canagliflozin Tablets were studied as monotherapy and as combination therapy to metformin, insulin, or other treatments. The treatment effects on HbA1c levels and one-hour postprandial glucose levels are summarized for four placebo-controlled, double-blind, randomized studies conducted in the United States. The placebo-subtracted treatment differences, which are summarized below, were statistically significant for both variables in all of these studies.

Study 1: (n=584) This study showed that canagliflozin caused a significant reduction in blood sugar soon after taking canagliflozin. This was true at both doses of 100 mg canagliflozin as well as with 300 mg of canagliflozin. HbA1c levels dropped by 0.8 mg/dl with the 100 mg treatment and by 1.0 mg/dl with the 300 mg treatment.¹

Study 2: (n=20) Canagliflozin reduced postprandial plasma glucose by 35% and insulin excursions by 43% in this study (P < 0.001 for both). It also increased urinary glucose excretion (UGE_{0-6h}, 18.2 ± 5.6 vs. <0.2 g; P < 0.001). It reduced blood glucose by increasing glucose excretion.⁶

Study 3: (n=1450) Canagliflozin at 100 mg and 300 mg reduced A1c levels by -0.65% and -0.74%, respectively, over a treatment period of 104 weeks. Also, it reduced systolic blood pressure by -2.0 mmHg with the 100 mg dose and by -3.1 mmHg with the 300 mg dose.⁷

Study 4: (n=4401) Canagliflozin was generally well tolerated⁸. Adverse events related to the kidneys were lower with canagliflozin treatment of 100 mg, with an incidence of 60.2 per 1,000 vs an rate of 84.0 per 1,000 of the control group.⁹

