6.4 Rationale and Hypothesis

Canagliflozin is a prime candidate to reduce glucose spikes and blood sugar. It has consistently acted to treat type 2 diabetes and has been shown to improve biomarkers such as fasted glucose and glucose spikes.

The current FDA-approved use of the drug is for use together with diet and exercise to treat type 2 diabetes. Canagliflozin is sometimes used in combination with insulin or other diabetes medications taken orally. It is routinely prescribed at equal or higher doses than the ones proposed in this trial.

AgelessRx Trial doses: 100 mg and 150 mg doses, taken every day and every-other day, respectively.

FDA-approved dose: Maximum recommended dose: 300 mg once daily.

Some possible side effects at the FDA-approved doses include hypoglycemia, indigestion, nausea, UTI, increased urination or thirst, hypotension, ketoacidosis, dehydration, and headache. The doses we propose have potential for some side effects, though the drug is generally well tolerated.

This trial will use a lower dose than the maximum one recommended by the FDA. We are using a maximum of 150 mg in one day vs the maximum of 300 mg each day recommended by the FDA. At this smaller dose, side effects are less common⁸. This dose has been shown to be generally safe.

Our hypothesis is three-fold:

1. Canagliflozin can be used safely and is well tolerated at doses of 100 mg per day or 150 mg every two days in healthy, non-diabetic individuals.
2. Usage of canagliflozin at these doses can effectively reduce glucose spikes (and their detrimental effects) and blood sugar levels measured by CGM in a healthy population.
3. Usage on alternate days will be effective as measured by our endpoints.

7. Objectives

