7.2 Secondary Objective

To assess the tolerability and side effects of the dosing protocol, and measure urinary glucose excretion.

8 Experimental plan

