8.3 Number of Centers and Subjects

We will recruit up to 20 healthy participants to participate in the study. Online prescriptions will be provided by [name] via the AgelessRx website (www.agelessrx.com). Our partner pharmacy with the ability to ship to most states nationwide will provide the prescriptions and CGMs to participants. Efficacy testing will be performed by AgelessRx. To measure glucose, the Abbott Laboratories Freestyle Libre CGM (<https://www.freestyleprovider.abbott/us-en/freestyle-libre-2.html>) will be used. For urinalysis, Access Medical Labs Glucose, Urine (<https://www.rupahealth.com/lab-tests/access-medical-labs-glucose-random-urine#description>) will be used.

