10.3 Safety and efficacy evaluations

The primary endpoint, average glucose, will be assessed by examining blood glucose (mg/dL) area under curve as measured by CGM. Glucose data on days without canagliflozin treatment will serve as a control.

The secondary endpoints of safety and tolerability and urinary glucose excretion will also be assessed. Safety and tolerability will be measured by adverse event reporting, blood pressure monitoring, and by comparing treatment tolerability survey results with control tolerability results through subjective surveys. Urinary glucose excretion will be measured by at-home glucose testing strips.

11 Investigational Product

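### Urinary glucose excretion is a secondary endpoint, but the plan gives two conflicting methods and neither, as described, measures an amount excreted

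*Combined protocol and SAP*

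**What the plan says.** Section 7.2 sets the secondary objective: "To assess the tolerability and side effects of the dosing protocol, and measure urinary glucose excretion". Section 10.3 repeats it as an endpoint: "The secondary endpoints of safety and tolerability and urinary glucose excretion will also be assessed". The Synopsis also lists urinary glucose as an efficacy criterion.

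The method is described in three places:

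- **Section 10.3:** "Urinary glucose excretion will be measured by at-home glucose testing strips".
- **Section 8.3:** "For urinalysis, Access Medical Labs Glucose, Urine". The link given there contains "access-medical-labs-glucose-random-urine".
- **Synopsis, Methodology:** four urine collection kits per participant. Kit #1 is on Day 7, before any drug. Kits #2 to #4 are on Days 15, 16 and 17, at 24, 48 and 72 h after the last dose; the last entry reads "Day 17: 72h after final dose, Participant completes Urine Collection Kit #4". What a kit contains is not stated.

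Section 6.2 reports the background evidence on this measure ("It also increased urinary glucose excretion") as grams over a timed 0-6 h interval: 18.2 ± 5.6 g against less than 0.2 g.

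**The concern.** There are two problems. First, a strip read at home and a laboratory assay are different measurements, and the plan does not say which one supplies the endpoint or how either relates to the kits. Staff could not tell which result to analyse.

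Second, excretion is an amount over time. A strip or a random specimen gives the concentration in one sample, which also depends on how dilute the urine is. To get from concentration to amount one needs a collection interval and a volume. To adjust for dilution one needs something like creatinine. None of these appears in the text available.

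The kits are the only urinary evidence on how long the effect lasts after each regimen, with one kit per time point and 10 participants planned per arm. If concentrations are reported as excretion, the trial could describe the persistence of excretion, or a difference between regimens, without having measured it.

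**Working it through.** The plan gives no figure of its own to reproduce for this endpoint, so the check compares the sections and then asks how far dilution alone can move a reading.

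**1. What is needed and what is given**

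| Needed for excretion | Found in the text available |
|---|---|
| One method | Two: strips (10.3), laboratory test (8.3) |
| Collection interval | None; the 8.3 link indicates a random specimen |
| Urine volume | None |
| Creatinine or other dilution adjustment | None |
| Sampling time | Nominal for Kits #2 to #4 (hours after last dose); none within Day 7 for Kit #1 |

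**2. Same excretion, different concentration**

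Inputs: 18.2 g and less than 0.2 g over 0-6 h (section 6.2). The urine volumes are assumptions, because the documents give none.

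Concentration (mg/dL) = grams × 1,000 / (litres × 10)

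| Assumed volume | 18.2 g | 0.2 g (upper bound) |
|---|---|---|
| 0.25 L | 7,280 mg/dL | 80 mg/dL |
| 0.5 L | 3,640 mg/dL | 40 mg/dL |
| 1.0 L | 1,820 mg/dL | 20 mg/dL |

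Identical excretion gives a 4-fold range of concentration (7,280 / 1,820) over these volumes.

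**3. Same concentration, different excretion**

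Grams per day = mg/dL × 10 × litres per day / 1,000. A reading of 1,000 mg/dL, taken as the day's average, corresponds to 10, 15, 20 or 30 g/day at an assumed 1, 1.5, 2 or 3 L/day. That is a 3-fold range from one reading.

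**4. Effect on a change between kits**

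Suppose excretion halves from 18.2 g to 9.1 g while volume falls from 1.0 L to 0.5 L. Both samples then read 1,820 mg/dL and the decline disappears. Suppose instead that excretion stays at 18.2 g while volume rises from 0.5 L to 1.0 L. The reading then falls from 3,640 to 1,820 mg/dL and a halving appears that did not happen. The 18.2 g is a 0-6 h value used only to show the mechanism; it does not predict levels at 24 to 72 h.

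**5. What a spot test can still show**

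The background contrast is at least 18.2 / 0.2 = 91-fold. Even with the most unfavourable pairing in the table (1,820 against 80 mg/dL), the ratio is 22.75. Glucosuria of that size would survive a 4-fold dilution range.

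**6. Specimens**

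20 participants × 4 kits = 80 at most.

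**The case against.** Several points on the other side stand.

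- **Spot sampling is inferred.** The word random occurs only inside a link, and the kits are undefined. The Synopsis refers to a materials list that is not in the text available, and the study design figure is not shown. A timed collection is not ruled out, but none is described.
- **Timing is partly specified.** Kits #2 to #4 are tied to the last dose, and doses are taken with the first meal. Only the Day 7 sample has no time of day.
- **The magnitudes rest on assumed volumes**, and the one documented amount is for 0-6 h, while the post-drug kits fall at 24 to 72 h.
- **No urine test is planned.** Section 13 names no analysis for urine, so an unsupported claim about persistence or arms is a risk, not something the plan states.

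A reader might go further and infer a systematic bias: section 6.4 lists "increased urination or thirst" as a possible side effect, so post-drug urine would be more dilute than the Day 7 sample, perhaps differently in each arm. The arithmetic would be simple: volume higher by an assumed 10%, 25% or 50% makes the post/pre concentration ratio 0.91, 0.80 or 0.67 of the true excretion ratio. The documents do not support this inference. No kit falls on Days 8 to 14, so no post-baseline sample is scheduled during dosing. Section 6.4 gives no size for the effect, does not say that it lasts 24 to 72 h after the last dose, and says that side effects are less common at the lower trial dose. Nothing is said about a difference between arms.

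A reader might also infer that the urine data would be worthless. The 91-fold contrast argues against that.

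None of this removes the conflict between sections 8.3 and 10.3 or supplies the missing interval, volume or creatinine.

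**Conclusion.** The concern holds in a limited form. The conflict of methods is on the face of the text and needs no assumption. That neither method yields excretion follows from what is described, on the reading that the kits are single samples. If a timed collection was intended, the plan has to say so.

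The consequence is that the urine results would support a statement about whether marked glucosuria is present. They would not reliably support one about the amount excreted, the size of any change across the three post-drug kits, or an arm difference. Over the assumed volumes of 0.25 to 1.0 L, dilution alone spans 4-fold; the true spread in this trial is not known from the documents. A directional bias from the drug is not established.

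The matter is confined to a secondary endpoint, since the primary endpoint is glucose by continuous monitor. It should be fixed before the first kit is used, because volume or creatinine that was not obtained cannot be recovered once specimens are discarded.

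**What to change.** Reconcile the Synopsis, section 8.3 and section 10.3 as follows:

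1. Use one quantitative laboratory method for all four kits in both arms, and delete the strip sentence in section 10.3. State what a kit contains.
2. Collect the Day 7 sample at the same time relative to the first meal as the Day 15 to 17 samples.
3. Add creatinine on the same specimen and report the endpoint as a urine glucose-to-creatinine ratio. The ratio adjusts for dilution but is not an amount over time, so it should not be described as grams excreted.
4. If creatinine is not added, rename the endpoint *spot urine glucose concentration* in the Synopsis and in sections 7.2 and 10.3, and draw no conclusion about the amount excreted.
5. If a timed collection was intended, state the interval and record the volume; grams per interval can then be reported.

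The cost is protocol wording plus one further assay on at most 80 specimens. The documents give no price and do not say whether the laboratory can run creatinine on this specimen, so that needs confirming. Renaming requires no assay; its cost is a narrower claim.

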11.1 Investigational Drug

Canagliflozin is an SGLT2 inhibitor. It is known under the name Invokana, when mixed with other compounds. It is chemically known as (2S,3R,4R,5S,6R)-2-[3-[[5-(4-fluorophenyl)thiophen-2-yl]methyl]-4-methylphenyl]-6-(hydroxymethyl)oxane-3,4,5-triol. It has a molecular weight of 444.52 g/mol and is an off-white powder. It is used to treat type 2 diabetes mellitus (a condition in which the body does not use insulin normally and therefore cannot control the amount of sugar in the blood). It works by inhibiting a sodium-glucose pump in the kidneys, SGLT2, leading to increased glucose excretion through urine. This helps reduce blood glucose levels as glucose is not reabsorbed into the blood.

11.2 Control Drug

No placebo will be used in this trial.

11.3 Dosing and Administration

11.3.1 Dose Escalation, Dose Adjustments, Stopping Rules

Participants will receive 100 mg tablets or 300 mg tablets, broken in half. There will be no dose escalation in this study. Dose adjustments or discontinuation of the drug can be made based on adverse events in a participant, which will be discussed in a phone call between the participant and Research Coordinator.

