10.1 Screening

Candidates will be offered the opportunity to participate in this trial after approval of canagliflozin prescription through the AgelessRx platform. Patients must proceed through medical intake, consent to participate, consultation with the AgelessRx medical team (synchronously or asynchronously, depending on the regulations of the state in which the candidate resides), and approval before receiving their treatment. Medical intake will be reviewed by the AgelessRx medical team and consent responses will be reviewed by the research coordinator. Once the candidate has been approved for their canagliflozin prescription and the patient has expressed interest and consented to participation, the AgelessRx research coordinator will contact the candidate for additional instruction. The medical intake and consent built into the patient process will include inclusion/exclusion screening criteria and will serve as a screening tool for medical and research personnel. The consent language built into the patient intake workflow can be found in Appendix A. Identity validation will occur prior to product intake submission and will be verified following consent completion, as a photo of self and I.D. are required before the patient may proceed. Informed consent will be captured via free text name entry within the consent questionnaire.

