11.4 Concomitant Medications

If participants fit eligibility criteria but are on other medications, they should continue to take those at the prescribed dosages. They will be instructed to tell their other physicians, medical providers, and pharmacists of their enrollment in the trial. Any changes to concomitant medications or any planned surgery should be discussed with the PI immediately.

12 Adverse Event Reporting

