12.2 Serious Adverse Events

Serious adverse events (SAE): any AE that results in death, is life-threatening, requires inpatient hospitalization, is persistent, or causes significant disability/incapacity, or causes a congenital anomaly or birth defect.

Adverse events will be graded according to the system below:

1. Grade 1: Asymptomatic or mild symptoms; clinical or diagnostic observations only; no intervention indicated (e.g. headache, nausea, abdominal discomfort).
2. Grade 2: Moderate; minimal, local or noninvasive intervention (e.g. vomiting, diarrhea, shortness of breath).
3. Grade 3: Severe; or medically significant but not immediately life threatening; hospitalization or prolongation of hospitalization indicated; disabling (e.g. dehydration, hypotension).
4. Grade 4: Life-threatening ; urgent intervention indicated (e.g. respiratory failure, myocardial infarction, liver failure).
5. Grade 5: Death related to an AE.

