12.3 Reporting of Adverse Events

12.3.1 Routine

The principal investigator will be notified about any adverse events. Furthermore, this information will be obtained through monitoring forms sent out to participants.

The Principal Investigator will document this information in the participant's medical record. Participants will be asked to report any serious adverse event immediately to the Principal Investigator. This can be done by email or phone (after hours phone number is available).

AEs will be documented using standard AE reporting (FDA regulations 21CFR314.80 and 21CFR213.32(s)). Both expected (already known) and unexpected AEs will be reported.

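### Section 11.3.1 gives no clinician the decision to adjust or stop study drug for an adverse event; secondarily, the 10.3 control rule, read literally, takes in Arm B's off-days and days after an early stop

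*Combined protocol and SAP*

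**What the plan says.** Section 11.3.1 rules out dose escalation. It then allows study drug to be adjusted or discontinued on account of a participant's adverse events, "which will be discussed in a phone call between the participant and Research Coordinator". Its title includes stopping rules, but it gives neither a threshold nor a decision-maker.

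Other sections assign roles more clearly. On other medicines, 11.4 says "Any changes to concomitant medications or any planned surgery should be discussed with the PI immediately". On screening, 10.1 says "Medical intake will be reviewed by the AgelessRx medical team and consent responses will be reviewed by the research coordinator". On adverse events, 12.3.1 says "The principal investigator will be notified about any adverse events", has the PI record them, and adds "Participants will be asked to report any serious adverse event immediately to the Principal Investigator", by email or by phone with an after-hours number. Section 8.1 asks for seven tolerability surveys, one per day once dosing begins. Under 9.4, participants withdraw by contacting the PI.

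For the primary endpoint, 10.3 says "Glucose data on days without canagliflozin treatment will serve as a control". Section 8.1 describes the week before dosing as baseline but does not say that it is the only control.

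**The concern.** Section 6.4 names among the possible side effects at FDA-approved doses "hypotension, ketoacidosis, dehydration, and headache", and 12.2 uses dehydration and hypotension as Grade 3 examples. Whether a participant with such a complaint should continue, reduce or stop is a medical decision. As written, it could be settled after a call with the coordinator, with no clinician's decision on record. Participation is wholly by telemedicine, ages run to 85, and stable hypertension or coronary artery disease is allowed (9.2). The call may therefore be the only live contact before the next dose.

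The 10.3 issue is separate and secondary. If the control set includes days that may still carry drug effect, the estimated effect on glucose shrinks toward zero. It would do so in the alternate-day arm in particular, whose effectiveness is the third hypothesis in 6.4.

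**Working it through.** **Who decides.** No arithmetic applies here, so the sections are set side by side.

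| Matter | Who is named | Timing | Is a decision assigned? |
|---|---|---|---|
| Study-drug adjustment or stop (11.3.1) | Participant and Research Coordinator | None stated | No |
| Other medicines, surgery (11.4) | PI | Immediately | Discussion with the PI |
| Medical intake (10.1) | Medical team | Before treatment | Yes, approval |
| Any adverse event (12.3.1) | PI | None stated | No; notified and records |
| Serious adverse event (12.3.1) | PI, told by the participant | Immediately | No |
| Withdrawal from the study (9.4) | PI, told by the participant | Any time | The participant's own choice |

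Changes to other medicines go to the PI at once, while changes to the study drug do not. Immediate reporting depends on the participant seeing the event as serious. The Grade 2 examples in 12.2 (vomiting, diarrhea, shortness of breath) need not meet the serious definition in the same section. Arm A doses every 24 h and Arm B every 48 h, within a course of 7 days (Days 8-14). A notification with no time limit can therefore arrive after the next dose, or after the last one.

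**Control days under the literal reading of 10.3.** The inputs are the schedule in the Synopsis and 8.1. It is assumed that CGM data cover Days 1-14 and that each day has equal weight.

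- Arm A takes 7 doses on Days 8-14. A completer has 14 - 7 = 7 control days, all before the first dose.
- Arm B takes 4 doses on Days 8, 10, 12 and 14. A completer has 14 - 4 = 10 control days: Days 1-7 plus off-days 9, 11 and 13.
- After an early stop, the later days join the control as well. For example, an Arm A participant who stops after the Day 10 dose and keeps the sensor on has 7 + 4 = 11 control days, 4 of them after the stop.

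**Size for an Arm B completer.** Let E be the effect on a dosed day relative to a truly drug-free day, and r the fraction of E that remains on each off-day. The documents give no value for r, so it is assumed to lie between 0 and 1.

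- Mean effect on dosed days: E
- Mean effect carried by the control: (7 × 0 + 3 × rE)/10 = 0.3rE
- Contrast: E - 0.3rE = E(1 - 3r/10)

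| r | Shrinkage, 3r/10 |
|---|---|
| 0 | 0% |
| 0.25 | 7.5% |
| 0.5 | 15% |
| 1 | 30% |

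No early stop is needed for this. An Arm A completer has no such shrinkage, so at any r above 0 the two arms are judged against different comparators. With Days 1-7 as the control in both arms, the control carries 0 and the contrast is E.

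**The case against.** On safety, 11.3.1 says that the change is discussed on the call; it does not say that the coordinator decides. Any change under 11.3.1 is by definition based on an adverse event, and 12.3.1 requires the PI to be told of every adverse event. There are also daily surveys, monitoring forms, an after-hours number, withdrawal through the PI and medical approval of each prescription. Diuretics are excluded (9.3), and 6.4 says that side effects are less common at the smaller dose. All of this stands and makes the gap narrow. A reader might infer that the coordinator rules on dosing, or that the PI is kept out of adverse events; the documents support neither. What the safeguards do not supply is a named decision-maker, or a time limit for events not reported as serious.

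On the control rule, 8.1 calls the first week baseline, so Days 1-7 may be what was meant. That is fair, but 10.3 does not say so. The post-stop part also needs someone to stop early and go on wearing the sensor, which the plan neither requires nor rules out. The off-day part needs neither. A reader might take the urine kits at 24, 48 and 72 h after the last dose as proof that the glucose effect persists. They show that the period is of interest, not that CGM glucose stays lowered.

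**Conclusion.** The safety point holds and carries most of the weight: no section gives a clinician the decision to adjust or stop study drug. It rests on the text alone and needs no number. Its reach is limited to events not reported as serious, during a 7-day course.

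The control-rule point holds as a secondary one, on the literal reading of 10.3. Its size is 0 to 30% shrinkage of an Arm B completer's contrast, depending entirely on the assumed r and on r being equal across the three off-days. With no residual effect it is zero. It would be wrong to conclude that the rule is harmless as long as nobody stops, because Arm B's off-days are scheduled for everyone in that arm. The 30% is the upper end of an assumed range, not an expected bias. The documents give no stop rate, so no figure is put on the days after an early stop.

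**What to change.** In 11.3.1, state that the PI or a delegated clinician of the medical team decides any adjustment or stop of study drug, and that the coordinator relays the adverse-event call to the PI the same day, before the next dose. This takes one or two sentences and slightly more PI and coordinator work, with no extra visits or samples.

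In 10.3, state that the control is the pre-dose period, Days 1-7, for every participant in both arms. An Arm B completer then has 7 control days instead of 10, all of them before dosing, so a drift between the two weeks cannot be separated from the drug effect. Arm A completers are already in that position. How off-days and days after a stop enter the treatment side is a choice of estimand. The sponsor should state it, but this point does not prescribe it.
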